10.11.2 Maintenance of Blinding

Systems for reporting safety events assessed as "serious" and "related" (i.e. Related SAEs and RUSAEs), should, as far as possible, maintain blinding of individual clinicians and of trials staff involved in the day-to-day running of the trial. SAE forms allow reporting investigators to make an assessment of causality without having to unblind the participant; breaking the blind will only take place where information about the participant's trial treatment is clearly necessary for the appropriate medical management of the participant.

Cases that are considered serious, unexpected and possibly, probably or almost certainly related to one of the trial therapies (i.e. possible RUSAEs) would have to be unblinded at the LCTC prior to reporting to onward reporting.

Unblinding procedures are detailed in section 9.4.

10.12 Safety Reporting Responsibilities – LCTC

The trial Sponsor, Manchester University NHS Foundation Trust, have delegated to LCTC the duty of onward reporting of safety events to REC. SOPs will be followed to ensure appropriate reporting as detailed below.

All "serious" safety events will be forwarded to the CI or authorised delegate by LCTC within 24 hours of receiving the minimum information from site.

The CI or authorised delegate will review information provided by site and for all events assessed as "related" will provide an assessment of "expectedness".

Safety events that are assessed as "serious", "related" and "unexpected", i.e. RUSAEs, will be onward reported by LCTC to the ethics committee **within 15 days** of the LCTC first becoming aware of the event.

Additionally, RUSAEs will be reported to the trial Sponsor, PIs of participating sites, and relevant product manufacturer, Nutricia or Sharp.

A list of all safety events recorded for the trial will also be reported annually by LCTC to the ethics committee and IDSMC.

Any concerns raised by the TSC or IDSMC or inconsistencies regarding safety reporting noted at a given site may prompt additional training at sites, with the potential for the LCTC to carry out site visits if there is suspicion of unreported AEs or SAEs in patient case notes. Additional training will also be provided if there are unacceptable delays in safety reporting timelines.

10.12.1 Overdose

The trial product for all arms is food, hence no toxicity is expected. However, an overdose may occur in the OIT arm. If a participant has a large amount of the trial product, there is an increased chance of an allergic reaction. Parents will be well informed of this risk and they will have the necessary medication and training to recognise and treat an allergic reaction. The risk will further be mitigated by parents in the OIT arm being advised to use routine care formula to give to the infant as add-on to the trial formula if the infant is still hungry after having the maximum allowed dose of trial formula.

10.12.2 Safety reports

Safety reports will be generated during the course of the trial which allows for monitoring of safety events, including reporting rates and safety events across sites. The LCTC will prepare Annual Progress Reports (APRs) containing a list of all SAEs for submission to the REC. If any safety reports identify issues that have implications for the safety of trial participants, the PIs at all participating centres will be notified.

10.13 Contact Details and Out-of-hours Medical Cover

All local PIs should ensure to delegate at least one other appropriately trained (in the study and in GCP) medically qualified doctor for assessment of adverse events, safety reporting and making medical decisions in their absence.

The CI or delegate are able to provide medical advice in relation to participation during office hours, using the contact details listed at the beginning of this document.

Emergency and out-of-hours medical care will be in line with usual NHS arrangements and local standard practice. All parents will be provided with a copy of the PISC which includes information about their child's participation and contact details for the local research team who may be contacted if necessary.

11 STATISTICAL CONSIDERATIONS

11.1 Introduction

Separate statistical analysis plans for interim and final analyses will be developed prior to any comparative analyses. The main features of these analyses are included here in the protocol.

11.2 Method of Randomisation

Participants will be equally randomised to eHF or pHF (1:1 ratio) using a secure (24-hour) web-based randomisation programme, controlled centrally by LCTC to ensure allocation concealment. Randomisation lists will be generated using block randomisation with random variable block length, stratified by site and initial tolerance to pHF. The lists will be produced by an independent statistician (who is not otherwise involved in the DREAM study) at LCTC.

11.3 Sample Size calculation

We have set high inclusion thresholds for SPTs/IgE, to recruit infants with a low chance to 'spontaneously' outgrow CMA (that is, to outgrow CMA while they are under normal care-eHF feeding, as is the case for our control group). Therefore, although population-based studies report a high rate of up to 75% spontaneous CMA resolution [5, 65, 66], in patients meeting our strict criteria only 37% developed tolerance by age four in one study [29] and only 20-30% by 3 years of age in three other studies [30, 67, 68]. We therefore expect spontaneous resolution (for the 'normal care' group) to be ~30% and allowed for 35% (closest to the highest reported) to ensure that the study will be sufficiently powered even in the worst-case scenario.

Regarding the expected resolution rate for the active intervention (pHF) group, to date there is no study using pHF for free feeding and there is no evidence for an expected rate. Although CM OIT has a success rate of 65%-90% [36-42] our study differs from CM OIT in that we are not giving normal CM but a less allergenic form (and therefore one would expect lower rates of CMA resolution in our trial due to exposure to less CM proteins); on the other hand, our trial also differs from CM OIT in that we are not giving the OIT product in small doses but in large quantities (freely), and therefore one would expect higher rates of resolution in our trial due to exposure to more protein. In any case, to power our study reliably we assume that the resolution rate for the intervention group should be at the lower end of the reported rates for CM OIT (65%). To ensure that the study will be sufficiently powered even in the worst-case scenario, we calculated the power on an expected 60% size effect for the pHF group. Indeed, a study where processed CM (baked milk) was used for desensitisation returned a size effect of 60% [53], further indicating that this would be an appropriate effect size.

A two-group chi-squared test with a 0.05 two-sided significance level will have 90% power to detect the difference between a proportion of 0.35 in the eHF group and a proportion of 0.60 in the pHF group (odds ratio of 2.786) when the sample size in each group is 82. Allowing for 20% attrition, a total of 206 patients will be randomised.

11.3.1 Feasibility (attaining recruitment targets)

1st Recruitment pathway – Feasibility study

We have conducted an ethically-approved feasibility study regarding the 1st recruitment pathway (Bounty), to get insight about: **i.** the potential number of surveys that will be filled in and submitted by parents; and **ii.** The number of infants that will be eligible for the next step (Hospital screening visit–V1).

Email contact details are currently available from Bounty for the catchment area of the study partners for roughly **35,000** infants between 6-12 months of age. Postal details for those with no email address are also available for roughly **11,000** infants, for a total of about **46,000** infants. To reach these infants Bounty will send e-mails (and letters if appropriate) approximately every 6 months (six times overall in the three-year recruitment period); therefore, throughout the whole recruitment period we will reach a total population of 46,000 x 6 = **276,000** infants of appropriate age for the study. Assuming that 2% of them have immediate CMA, this means that throughout the study we will have access to 5,520 age-appropriate infants with CMA through Bounty alone.

We have conducted a feasibility study in order to get insight about the actual numbers of potentially eligible infants that we will be able to invite to V1 from this population. For the feasibility study we sent out 8000 emails containing a link to the online DREAM recruitment survey to parents of 6-12-month-old infants identified by Bounty in cities where we will be recruiting.

The results of the feasibility study were as follows:

- i. **30%** of parents (2349/8000) opened and read the email containing the survey link.
- ii. **4.5%** of those (103/2349), filled in and submitted the survey.
- iii. **17.5%** of those (18/103), were deemed to be eligible for an invite to the screening visit- V1.

The above evidence furnished by the feasibility study has informed the Bounty recruitment pathway as follows: We expect that: **i.** 30% of the parents reached through Bounty will open their mail **(82,800** out of 276,000); **ii.** 4.5% of those will fill in and submit the survey (**3726** out of 82,800); and **iii.** 17.5% of those (652 out of 3726 infants) will be eligible for the screening visit –V1 from the 1st pathway.

Assumptions from all pathways

After being screened at V1, potential participants need to meet the inclusion criteria to proceed to the free feeding (or the OIT module). **The assumptions for this stage are as follows: i.** We assume that no more than **25%** of the infants screened at V1 will meet the IgE or SPT inclusion criteria (conservative estimation). These infants will continue to the next step (pHF challenge-V2). **ii.** We expect that **~33%** of these infants will react to pHF at the pHF challenge–V2 [59], and will therefore be recruited as 'pHF– reactive, CM protein-allergic'. **iii.** From the remaining infants (those not reacting to pHF) we assume that **50%** will react to CM in the milk challenge–V3, and will therefore be recruited as 'pHF–tolerant, CM protein-allergic' (conservative assumption, as for this age range and these specific IgE levels, clinical reactivity is over 90% [69]).

The above conservative assumptions suggest that, for 206 infants to proceed to free feeding/OIT module, we need **1241 infants** to be reviewed at the screening visit-V1. 652 infants will reach V1 from the first recruitment pathway (Bounty). The remaining infants will be invited to V1 through the other recruitment pathways.

11.4 Interim Monitoring and Analyses

Accumulating data will be presented at regular intervals (at least annually) for review by an IDSMC. These analyses will be performed at the Clinical Trials Unit. The IDSMC will be asked to give advice on whether the accumulated data from the trial, together with results from other relevant trials, justifies continuing recruitment of further patients or further follow-up. A decision to discontinue recruitment, in all patients or in selected subgroups will be made only if the result is likely to convince a broad range of clinicians including participants in the trial and the general clinical community.

11.5 Analysis Plan

The trial will be analysed using the International Conference on Harmonisation E9 guidelines and reported using the 'Consolidation Standard of Reporting Trials' (CONSORT) guidelines.

The analyses of primary and secondary outcomes will use the principle of intention to treat, based on all the randomised participants, as far as is practically possible. A p-value of 0.05 or less will be used to declare statistical significance for all analyses and results will be presented with 95% confidence intervals. Baseline characteristics will be presented but no comparisons will be undertaken, rather the clinical importance of any imbalance will be noted.

Binary data (including the primary outcome of the proportion of patients who are no longer allergic to CM protein) will be reported in terms of relative risk and analysed using logistic regression, adjusted for the stratification factors (site and initial tolerance to pHF). There will be a secondary analysis of the primary outcome using a chi-squared test for consistency with the sample size calculation. There will also be two subgroup analyses of the primary outcome, the first will include patients who initially tolerate pHF and the second will include patients who did not initially tolerate pHF.

Continuous data will be presented as means and standard deviations and analysed using two-sample t-tests (if data is skewed, medians and ranges will be presented, and analysis will be by Mann Whitney U tests). All related AEs and serious adverse events SAEs reported by the clinical investigator will be presented, identified by treatment group, but no formal comparisons will be made across the treatment groups.

Missing data will be monitored, and strategies developed to minimise its occurrence, however as much data as possible will be collected about the reasons for missing data and this will be used to inform the handling of missing data.

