have a protracted course in more patients than previously expected, who may also remain allergic in adulthood. These patients, as shown by the researchers, are mainly the moderate/severe allergics with high CM-specific IgE titre and/or large CM Skin Prick Test (SPT) results.

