6.1.1 Visit 1 Inclusion Assessments

- 1. Infant aged 6 to 12 months, inclusive.
- 2. Convincing medical history of *IgE-mediated* allergic reaction following ingestion of cow's milk formula, as determined by trial physician.
- 3. Infant fed with formula, either exclusively or mixed with breastfeeding.
- 4. Weight of at least 7.5kg.
- 5. Written informed consent by parent/legal guardian prior to completing any study-related procedure.
- 6. Titre of cow's milk-specific IgE in serum, equal or higher to 2 kU/L (collected at visit 1, confirmed prior to visit 2/3), at inclusion **or** wheal reaction of equal or over 5mm to SPT* to CM at inclusion

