8.4.1.1 VISIT 1 (Screening Visit)

Visit 1 will last up to 2-3 hours. In this visit, each participant's eligibility will be checked against the **inclusion and exclusion criteria** (see sections 6.1.1 and 6.2.1). Evidence for the participant's eligibility will be collected and recorded in the patient's medical records.

Participants will undergo the following assessments:

- 1. Obtain informed consent: See section 8.3.
- Demographics & full medical history and diet: Date of birth, birth weight, gestation time, gender, parity, race, number of siblings, family history of allergic disease (eczema-atopic dermatitis, Allergic rhinoconjunctivitis, asthma, and food allergy) and other epidemiological characteristics. Details of any personal history of disease with focus on asthma, urticaria and angioedema, atopic dermatitis, food allergies, and drug allergies. Concomitant medication.
- 3. Physical Examination, current medical history & vital signs: Weight, length, EASI Score & history of wheeze. The following will be confirmed to be normal and a statement to this effect recorded in the medical notes: general physical examination with chest auscultation, Peripheral arterial pulse, heart rate, systolic and diastolic blood pressure, respiratory rate, and oxygen saturation.
- 4. Skin prick tests: will be conducted for cows' milk using whole, fresh milk, egg, House dust mite mix, cat dander, 6 grass pollen mix.
- 5. Blood sample for antigen-specific IgE to the following antigens: IgE levels to CM (CM-IgE), Alpha lactalbumin (ALA-IgE), beta lactoglobulin (BLG-IgE), and casein (Cas-IgE).
- 6. Safety blood tests: The following will be confirmed to be normal and a statement to this effect recorded in the medical notes:

- Haematology: Full blood count
- Biochemistry: Liver function tests; Urea; creatinine.
- 7. Collection of blood samples for storing: These will be collected only where **consent** has been provided and processed and stored locally until transferred to the central laboratory.

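### Free improvement: the primary model is valid but leaves out baseline milk-specific IgE, which the protocol itself names as a marker of persistent allergy

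*Protocol*

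**What the plan says.** **The model.** Section 11.5 states that binary outcomes, including the primary one, are analysed by logistic regression "adjusted for the stratification factors (site and initial tolerance to pHF"). The only other analyses it names for the primary outcome are an unadjusted chi-squared test and two subgroup analyses by initial pHF tolerance. The adjustment set matches the randomisation in section 11.2, which is "stratified by site and initial tolerance to pHF".

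**The prognostic markers.** Section 3.1 says that the patients with a protracted course are "mainly the moderate/severe allergics with high CM-specific IgE titre and/or large CM Skin Prick Test (SPT) results". Section 11.3 uses the same idea to justify the control rate: "We have set high inclusion thresholds for SPTs/IgE, to recruit infants with a low chance to 'spontaneously' outgrow CMA".

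**The data.** Section 8.4.1.1 lists, at visit 1, "IgE levels to CM (CM-IgE), Alpha lactalbumin (ALA-IgE), beta lactoglobulin (BLG-IgE), and casein (Cas-IgE"). The table in section 7 places this sample and the skin prick test at visit 1, and randomisation at visit 3 or 4. Section 6.1.1 item 6 admits infants with "Titre of cow's milk-specific IgE in serum, equal or higher to 2 kU/L" or a wheal of at least 5 mm. There is a floor on either marker but no ceiling, and an infant who enters on the skin test may have an IgE below 2 kU/L.

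**The concern.** The variable that the protocol relies on to select its population and set its expected control rate is absent from the model that estimates the treatment effect. A baseline covariate that predicts the outcome, measured before randomisation, normally sharpens a treatment comparison and removes the part of a chance imbalance that it explains. Here the covariate is already scheduled, so leaving it out saves no visit and no blood sample.

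Two things are at stake, both modest. One is some power on the primary question. The other is how the result reads if the arms happen to differ in IgE. Section 11.5 says only that the clinical importance of an imbalance will be noted. An IgE-adjusted analysis added after such an imbalance was seen would be post hoc.

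**Working it through.** **Inputs from the protocol.** Rates 0.35 (eHF) and 0.60 (pHF), two-sided 0.05, 90% power, 82 per group, 20% attrition, 206 in total (section 11.3); 12 centres (section 2); 1:1 allocation (section 11.2).

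**Inputs that are assumptions.** The protocol gives no prognostic strength for IgE, so the odds ratio (OR) per SD of log IgE is varied from 1 to 4. Initial tolerance is given an odds ratio of 2.0 and a share of 50%. That share agrees with section 11.3.1: 33% react to pHF and half of the remaining 67% react to milk, so 0.33/(0.33 + 0.335) = 49.6% of those randomised are pHF-reactive. IgE and tolerance are taken as independent.

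**1. The stated sample size.** With mean rate 0.475,

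n = [1.960·√(2·0.475·0.525) + 1.2816·√(0.35·0.65 + 0.60·0.40)]² / 0.25² = (1.384 + 0.876)² / 0.0625 = 81.8, so 82 per arm.

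Power at 82 per arm is 90.1%. The odds ratio is (0.60/0.40)/(0.35/0.65) = 2.786. Attrition gives 82/0.8 = 102.5, so 103 per arm and 206 in total. The plan's figures reproduce exactly, with no IgE term needed.

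**2. Size of a chance imbalance.** With 82 per arm, the difference in mean log IgE has a standard deviation of √(2/82) = 0.156 SD, so its 95% range is ±1.96·0.156 = ±0.306 SD. At the edge of that range, an unadjusted odds ratio is shifted by a factor of about OR^0.306:

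| OR per SD of log IgE | Shift factor |
|---|---|
| 1.5 | 1.13 |
| 2 | 1.24 |
| 3 | 1.40 |
| 4 | 1.53 |

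These are edge-of-range figures on the odds ratio scale, to be set against the design value of 2.786.

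**3. Power with and without IgE.** 3,000 simulated trials per setting, 164 evaluable infants, 12 sites as fixed effects, arms roughly balanced within site and tolerance, marginal rates held at 0.35 and 0.60, Wald test of treatment:

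| OR per SD | Site + tolerance (planned) | Planned + log IgE | Gain (points) |
|---|---|---|---|
| 1.0 | 91.4% | 91.5% | 0.1 |
| 1.5 | 91.6% | 92.4% | 0.8 |
| 2.0 | 91.8% | 93.4% | 1.7 |
| 3.0 | 91.9% | 96.2% | 4.2 |
| 4.0 | 91.1% | 96.5% | 5.4 |

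Gains are taken from the unrounded results. If IgE carries no information, adding it costs nothing visible.

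**4. Type I error.** Under no treatment effect, the planned and enlarged models gave 5.1% and 5.4% at an odds ratio of 2 per SD, and 5.4% and 5.8% at 3. The Monte Carlo standard error is √(0.05·0.95/3000) = 0.4 points, so the two models are not clearly different. Both lie at or slightly above the nominal level.

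**5. Model size.** Expected events are 82·0.35 + 82·0.60 = 77.9. The planned model has 11 site terms, treatment and tolerance, which is 13 terms if site is a fixed effect. IgE makes 14.

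**The case against.** The strongest reply is that nothing here is wrong. Adjusting for the factors used in stratification is correct practice, sections 11.2 and 11.5 agree, and the power claim holds. All of that stands.

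Three further objections limit the size of the point:

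- **Severity is already partly in the model.** Section 9.1, on the OIT module, says pHF-tolerant infants may differ immunologically and may be likelier to outgrow the allergy. Tolerance is both a stratification factor and a covariate. As far as IgE tracks tolerance, the gain is smaller than in the table, which assumes independence.
- **The prognostic statement concerns a wider population.** Section 3.1 contrasts moderate or severe allergy with milk allergy at large, and section 11.3 then restricts entry to the former. The protocol gives neither the spread of IgE among enrolled infants nor its predictive strength within them.
- **The analysis plan may hold more.** Section 11.1 says the protocol gives only main features, and a supporting adjusted analysis could be in the unseen SAP. But the covariates of the primary model are stated in 11.5, so changing them means changing this text.

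A reader might go further and infer that chance imbalance in IgE makes the primary estimate biased, or that covariate adjustment is the trial's only protection. The documents do not support either. Imbalance under randomisation is ordinary sampling error, already covered by the confidence interval and p-value, and stratification by site and tolerance gives partial protection.

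**Conclusion.** This is a free improvement, not an error. The primary model is valid and reaches its stated 90% power. It leaves out a baseline variable that the protocol itself treats, together with the skin prick test, as a marker of persistence and already schedules before randomisation.

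The loss is about 1 to 2 power points if the odds ratio per SD of log IgE is 1.5 to 2, and about 4 to 5 points if it is 3 to 4, plus some protection against chance imbalance. These figures rest on assumed prognostic strengths and on independence of IgE and initial tolerance; with overlap they shrink. The direction is secure and the exact size is not.

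It would be an over-reading to call the trial underpowered or its planned estimate biased. The text also gives no basis for adding age as a covariate. The skin-prick wheal has an equal textual claim to be a covariate, since section 3.1 names the two with an and/or. It cannot stand in for a missing IgE value, because millimetres and kU/L are different scales.

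**What to change.** Before any comparative analysis, and without sight of accumulating results by arm, amend section 11.5 so that:

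- the primary logistic model includes, besides site and initial pHF tolerance, baseline log CM-specific IgE from visit 1 as a pre-specified continuous covariate;
- an occasional missing baseline IgE is filled by a simple rule that ignores arm, such as the overall mean of log IgE, so that no randomised infant is lost from the model for this reason;
- the model with the stratification factors only, and the chi-squared test, are kept as sensitivity analyses.

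One caution for reporting: adding a prognostic covariate to a logistic model changes the conditional odds ratio even when the arms are balanced. The models should therefore be compared on the relative-risk scale that section 11.5 already adopts, not by their odds ratios.

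The cost is a line or two in section 11.5 and matching text in the SAP. No extra infants, visits or measurements are needed, and the sample size stays as it is.

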8.8.2 Other efficacy assessments

- 1. The dose at which reactivity occurs in the DBPCFC will be recorded in the participant's medical notes and will be used to assess changes in the tolerance threshold of participants who will react to the DBPCFC (Positive challenge still CM allergic participants).
- 2. The maximum wheal size of the Skin prick test to milk by calculating the longest wheal diameter [60] between visits 1 and 8 will be recorded and can be used as a proxy to asses changes in CM sensitisation in participants.
- 3. The titres of specific IgE levels to cows' milk casein, a-lactalbumin and b-lactoglobulin between visits 1 and 8 will be assessed by CAP FEIA [61] locally at the sites, will be recorded and can be used as a proxy to asses changes in CM sensitisation in participants.
- 4. EASI scores for eczema will be recorded at all face-to-face visits to assess changes in eczema activity.
- 5. Information on wheeze episodes, wheeze-related use of systemic steroids, and wheeze-related hospitalisations during last 12 months (in the first visit) and since the last visit (all other occasions) will be recorded at all face-to-face visits to assess differences between the study product-randomised arm and the routine care-randomised arm.
- 6. Information for physician-diagnosed allergies to other foods will be recorded on visits 1 and 9, to assess differences in the development of allergies to non-CM foods between participants.

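### Continuous secondary outcomes are tested without the V1 baseline or the stratification factors, which gives up precision on five outcomes whose baselines are already collected

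*Protocol*

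**What the plan says.** For continuous outcomes, protocol section 11.5 (Analysis Plan) gives one rule: "Continuous data will be presented as means and standard deviations and analysed using two-sample t-tests". The exception is that "if data is skewed, medians and ranges will be presented, and analysis will be by Mann Whitney U tests". No covariate is named in either case. Section 11.5 does not say whether the quantity compared is the follow-up value or the change from baseline.

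Binary outcomes in the same section are "analysed using logistic regression, adjusted for the stratification factors (site and initial tolerance to pHF"). Section 11.2 explains why those two factors appear: randomisation is "stratified by site and initial tolerance to pHF".

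The baselines exist. The schedule in section 7 and section 8.4.1.1 put the skin prick test, specific IgE, weight, length and EASI at V1, and section 8.7.4.1 repeats all of them at V8. Section 8.8.2 describes "The maximum wheal size of the Skin prick test to milk by calculating the longest wheal diameter [60] between visits 1 and 8" and says of both wheal size and IgE that they "can be used as a proxy to asses changes in CM sensitisation in participants". It gives EASI a similar purpose. Section 8.9.1 has weight and height measured at all visits.

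**The concern.** The protocol collects a before-and-after pair for five continuous outcomes, says that three of them are meant to show change, and then names tests with no place for the baseline as a covariate. Variation between infants that was already present at entry stays in the error term, and a chance imbalance at baseline is not corrected. Entry is at 6 to 12 months, and the weight, IgE and skin test criteria in section 6.1.1 set only lower limits, so some spread at entry is built in.

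The stratification factors are also treated unevenly, being used for binary outcomes and dropped for continuous ones. The protocol itself expects initial pHF tolerance to matter: section 9.1 says pHF-tolerant infants may differ immunologically and may be more likely to outgrow the allergy anyway.

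At stake is the precision of the supporting evidence on sensitisation, eczema and growth.

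**Working it through.** **The plan's own figure.** Section 11.3 gives 82 per group for 0.35 against 0.60, two-sided 0.05, 90% power. The uncorrected chi-squared formula is

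n = [1.960 × √(2 × 0.475 × 0.525) + 1.2816 × √(0.35 × 0.65 + 0.60 × 0.40)]² / 0.25² = (1.3842 + 0.8763)² / 0.0625 = 81.8, so 82.

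With 20% attrition, 82 / 0.8 = 102.5, so 103 per arm and 206 in total. Both figures reproduce. They concern the primary binary outcome; no power is stated for any continuous outcome.

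**Inputs for the check.** 82 evaluable infants per arm (section 11.3). The correlation r between V1 and V8 values is not in the documents, so it is assumed over 0.3 to 0.7.

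**Formulas.** Set the variance of the follow-up value to 1.

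- t-test on follow-up values: variance 1.
- t-test on change scores: variance 2(1 − r), assuming equal variances at V1 and V8.
- ANCOVA: residual variance 1 − r².
- Narrowing of the CI against follow-up values: 1 − √(1 − r²).
- Narrowing against change scores: (1 − r²) / [2(1 − r)] = (1 + r)/2, so 1 − √((1 + r)/2).

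| r | ANCOVA variance | Change-score variance | CI narrower than follow-up t-test | CI narrower than change-score t-test |
|---|---|---|---|---|
| 0.3 | 0.91 | 1.40 | 5% | 19% |
| 0.5 | 0.75 | 1.00 | 13% | 13% |
| 0.7 | 0.51 | 0.60 | 29% | 8% |

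**In terms of power.** At 82 per arm, an unadjusted t-test on follow-up values has 80% power for a difference of (1.960 + 0.842) × √(2/82) = 0.44 SD. For that same difference (normal approximation):

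| r | Follow-up t-test | Change-score t-test | ANCOVA | Unadjusted n per arm matching ANCOVA, 82/(1 − r²) |
|---|---|---|---|---|
| 0.3 | 80% | 65.8% | 83.6% | 90 |
| 0.5 | 80% | 80.0% | 89.9% | 109 |
| 0.7 | 80% | 95.1% | 97.5% | 161 |

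These figures cover the baseline covariate only. They leave out any variance explained by the strata, which would add to the gain. They also leave out the degrees of freedom spent on site (12 planned centres, so 11 parameters), a small cost because blocked allocation limits imbalance between arms within site.

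**Which outcomes have a baseline.** Wheal size, specific IgE, EASI, weight and length do. The reactive dose, listed first in section 3.4.2, does not. The DBPCFC takes place only at V8 and V9 (section 8.8.1), the entry challenges are open, and pHF-reactive infants skip the cow's milk challenge (section 4).

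**The case against.** The strongest reply is that nothing here is invalid. Under 1:1 randomisation the unadjusted tests are sound, and ignoring stratification factors tends to make them conservative rather than to inflate type I error. The outcomes are secondary, section 8.8.2 presents wheal size and IgE only as proxies, and the protocol makes no power claim for them. All of that stands and limits the point to one of efficiency. It does not justify leaving out data already collected, and because section 11.5 names the tests, an SAP that used ANCOVA would depart from the protocol.

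Several stronger readings are tempting but not supported:

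- **That no use at all is made of baseline.** Section 8.8.2 speaks of changes, so the t-test may be meant for change scores. Both readings are therefore shown above; ANCOVA is the more precise under either.
- **That skewed outcomes are left without a confidence interval.** The section says "for all analyses and results will be presented with 95% confidence intervals", and a Hodges-Lehmann shift with its interval fits a Mann-Whitney analysis. The effect measure is unnamed, as is the criterion for skewness, but those are details the SAP may supply.
- **That the gain is as large as a 40% smaller standard error, or 2.78 times the sample size.** That needs r = 0.8 and the follow-up-value reading. On change scores the same r gives 1 − √0.9 = 5%, and 1/0.9 = 1.11 times.
- **That most follow-up variation is already present at baseline.** This needs r² above 0.5, so r above 0.71, and nothing in the document establishes it.
- **That every continuous outcome has a baseline.** The reactive dose does not.

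**Conclusion.** The point holds as a loss of precision on five secondary outcomes: skin prick wheal, specific IgE, EASI, weight and length. The stated tests are valid, but they ignore the stratification factors and do not condition on V1 values that the trial already collects.

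The direction is certain for any r above 0 on the follow-up reading and any r below 1 on the change-score reading. The size is not, because r is assumed: the confidence interval would be 5% to 29% narrower on the first reading and 8% to 19% narrower on the second, over r of 0.3 to 0.7. The change-score figures also assume equal variances at V1 and V8. The primary analysis, the 82 per group and the total of 206 are unaffected.

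**What to change.** In section 11.5, for the five outcomes with a V1 baseline, replace the t-test/Mann-Whitney rule by ANCOVA of the V8 value on arm, V1 value, initial pHF tolerance and site. Name V8 explicitly, because EASI, weight and length are recorded again at V9. Analyse specific IgE on the log scale and report a geometric mean ratio. Report the adjusted difference or ratio with its 95% CI for each outcome, and keep Mann-Whitney as a sensitivity analysis.

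State separately how the DBPCFC reactive dose is analysed, either adjusted for the stratification factors only or by a method of its own.

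The cost is about two sentences in section 11.5 and matching text in the SAP. No new data, visits or participants are needed. The change should be made before any comparative data are seen, in line with the timing that section 11.1 sets for the analysis plans.
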